Cover page

Official Title: An interactive advance care planning intervention to facilitate a good death for
cancer patients

NCT number: NCT01912846

Date of the Document: 2018/1/24

Specific Aims: The primary objectives of this 5-year randomized controlled trial (RCT) of a theory-based, tailored, multifaceted, interactive advance care planning (ACP) intervention are to examine the extent to which the proposed ACP intervention will (1) increase the congruence between terminally ill cancer patients' preferred and actual end-of-life (EOL) care, (2) improve quality of life (QOL), depressive and anxiety symptoms of patients and caregivers during the patient's dying process, and (3) enhance family caregivers' bereavement adjustment. The secondary objectives are to determine the effectiveness of the proposed ACP intervention in facilitating patients' prognostic awareness and EOL care discussions among patients, families, and physicians; in increasing patient-caregiver agreement on preferences for EOL care; and in reducing aggressive EOL care treatments for terminally ill cancer patients.

A randomized controlled trial with a tailored, multifaceted ACP intervention will be conducted on a convenience sample of 231 dyads of terminally ill cancer patients and caregivers with the same number of attention controlled group to evaluate the intervention's effectiveness.

We hypothesize that the proposed intervention will (1) facilitate terminally ill cancer patients' prognostic awareness; EOL care discussions among patients, family caregivers, and physicians; and patient-caregiver agreement on preferences for EOL care as death approaches; (2) reduce aggressive healthcare resource utilization at EOL; (3) increase congruence between the patient's preferred and actual EOL care; (4) improve QOL, depressive and anxiety symptoms of patients and family caregivers during the patient's dying process; and (5) enhance family caregivers' bereavement adjustment. We also hypothesize that the proposed intervention will facilitate patients' prognostic awareness and EOL care discussions among patients, families, and physicians; increase patient-caregiver agreement on preferences for EOL care; and reduce aggressive EOL care treatments for terminally ill cancer patients.

Eligibility criteria for terminally ill cancer patients: (1) diagnosed with a terminal stage disease that continues to progress with distant metastases and judged by their oncologists as

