procedures provided to subjects in the ACP intervention and attention-control groups will be reviewed by an independent research staff every 3 months to check the extent to which they are consistent with the group protocol. To this end, the research staff will interview randomly selected patient-caregiver dyads in each study group. Third, the workbook and video will be created systematically, starting with a review of the ACP literature in advanced cancer. The workbook content and overall video design will be reviewed for appropriateness and accuracy by 2 physicians specializing in cancer care, 1 ICU physician, 1 expert in palliative medicine, and 1 nurse with expertise in clinical decision-making.

Data collection procedures: Assessments will be performed prospectively and continue until patient death, loss to follow-up, study withdrawal, or when the patient can no longer be interviewed. An every-3-week time frame will be used in this study for repeated QOL and other outcomes assessments for both patients and their family caregivers bases on the review of literature to cover the most rapid change of patient physical conditions and demanding period of caregiving until the death of the patient. After each patient's death, a chart review and postmortem interview with patients' caregivers will be performed to confirm the type of medical care received at the EOL. Bereavement interviews will be conducted 1, 3, 6 and 13 months after the time of death in order to avoid contamination on the basis of anniversary grief reactions.

Data safety and management plan

An independent Data and Safety Monitoring Board (DSMB) will be organized to ensure patient safety throughout the trial as well as its validity and scientific merits. The DSMB will comprise a biostatistician experienced in statistical methods for clinical trials, a nursing researcher experienced in conducting randomized controlled trials, and a physician-scientist experienced in cancer care. The DSMB will monitor and address the following issues: (1) sufficient and appropriate enrollment of subjects, including compliance with the eligibility criteria for each dyad of terminally ill cancer patients and family caregivers, (2) appropriate

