The effectiveness of the intervention will be examined using intention-to-treat analyses with generalized estimating equations (GEE) or hierarchical generalized linear modeling (HGLM). Effectiveness of the intervention will be assessed in terms of (1) facilitating prognostic awareness, EOL care discussions, patient-caregiver agreement on preferences for EOL care, and congruence between patients' preferred and actual EOL care, (2) improving patients' and family caregivers' QOL, anxiety and depressive symptoms before the patient's death, and family caregiver bereavement outcomes, and (3) limiting aggressive healthcare resource utilization at EOL. In the intention-to-treat analyses, all participants will be analyzed in the study group to which they are initially allocated, regardless of whether they complete or withdraw from the study. The GEE/HGLM uses robust standard error estimates to take into account (1) within-subject correlations of the outcome variables during the study period, (2) unequal numbers of assessments among subjects, and (3) potential missing observations. In GEE/HGLM analysis, incompleteness of the outcome variables has only marginal influence on the results of longitudinal data analysis because GEE/HGLM involves fitting a generalized linear model to the marginal distribution of repeated outcomes.¹⁵¹

The congruence between terminally ill cancer patients' preferred and actual EOL care will be determined by comparing the agreement between preferences for EOL care elicited at the last assessment and actual EOL care. Preferences for each EOL care treatment will be dichotomized so that those who are "unsure" whether prefer a specific EOL care treatment will be counted as desiring that treatment because in most instances the clinical default is to provide

treatment unless specifically refused.⁷² In addition to the percentage of overall agreement, kappa coefficients will be computed to correct for the amount of agreement that can be expected by chance alone.¹⁵²

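### The rule for ending assessments does not say whose interviews stop once the patient cannot be interviewed; taken literally, it drops caregiver outcomes late in the dying process

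*Combined protocol and SAP*

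**What the plan says.** The two key sentences stand next to each other under Data collection procedures.

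- **Stop rule.** Assessments "continue until patient death, loss to follow-up, study withdrawal, or when the patient can no longer be interviewed". The subject is unqualified: it is not limited to patients, and caregivers are not excepted.
- **Schedule.** "An every-3-week time frame will be used in this study" for "repeated QOL and other outcomes assessments for both patients and their family caregivers". The reason given for the interval is "to cover the most rapid change of patient physical conditions and demanding period of caregiving until the death of the patient".

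Three other places bear on this.

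- **Specific Aims** lists among the primary objectives an improvement in quality of life and in "depressive and anxiety symptoms of patients and caregivers during the patient's dying process".
- **Statistical analysis plan** takes "family caregivers' QOL, anxiety and depressive symptoms before the patient's death" as outcomes, to be analysed by GEE or HGLM. On missing data it says that "incompleteness of the outcome variables has only marginal influence on the results of longitudinal data analysis".
- **Data collection procedures**, after the schedule, provides for a chart review and a caregiver interview after each death to confirm the care received, and for bereavement interviews at 1, 3, 6 and 13 months.

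Nowhere do the documents say that the last stop condition applies to the patient's own interviews only, or that the caregiver carries on after it is met.

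**The concern.** A caregiver does not lose the ability to answer when the patient does. If a data collector applies the stop rule as written, the caregiver's three-weekly interviews end on the day the patient's do. The caregiver then contributes nothing until after the death.

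The interval lost lies within the period that the caregiver objective targets, and within the period the three-weekly schedule is meant to cover. The observations would be missing because the patient has declined, which is plausibly related to how the caregiver is faring. Data not collected before the death cannot be recovered later: the interview after death is there to establish what care was given, and the bereavement interviews serve a separate objective.

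**Working it through.** The documents give no figure on this point to reproduce. The check is a comparison of texts, followed by a conditional count of visits.

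**1. What each reading does to a dyad that neither withdraws nor is lost.**

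| Patient | Stop rule taken literally | Last condition taken as patient-only |
|---|---|---|
| Interviewable up to death | Both followed to death | Both followed to death |
| Uninterviewable before death | Both stop at that point | Patient stops; caregiver followed to death |

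The readings differ only in the second row, and there only for the caregiver. The schedule sentence fits the right-hand column, since it names caregivers and gives coverage up to the death as its purpose. The stop rule, as worded, fits the left-hand column. No other section decides between them.

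**2. Which outcomes are exposed.** Caregiver quality of life, depressive symptoms and anxiety before the death are exposed. Bereavement outcomes are not, because those interviews are timed from the death. Nor is the record of actual end-of-life care, because the chart review follows each death.

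**3. How many visits.** Let g be the weeks from the point at which the patient can no longer be interviewed to the death. The documents do not give g, so these are assumed values. On a 3-week schedule the caregiver visits lost per affected dyad are about g / 3:

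- g under 3 weeks: 0 or 1 (for example 2 / 3 = 0.67 on average)
- g = 3: 3 / 3 = 1
- g = 6: 6 / 3 = 2
- g = 12: 12 / 3 = 4

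**4. Why a percentage is not available.** The share of an affected caregiver's pre-death visits that is lost is roughly g divided by the length of pre-death follow-up, which the documents also do not give. For g from 2 to 6 weeks:

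- follow-up assumed to be 13 weeks: 2/13 = 15% to 6/13 = 46%
- follow-up assumed to be 26 weeks: 2/26 = 8% to 6/26 = 23%

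The share across the trial would be smaller again, by the proportion of dyads whose patient becomes uninterviewable before death. That proportion is unknown.

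**5. Whether the analysis copes.** Unweighted GEE is in general valid only when data are missing completely at random. Stopping the caregiver because the patient has declined does not meet that condition. Robust standard errors address the variance, not bias from selective loss. Adjustment for time-varying confounders might help if the patient's condition were among them, but the confounders are not listed. The SAP leaves the choice between GEE and HGLM open and describes no sensitivity analysis.

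**The case against.** The best answer is that the text can be read consistently. The disputed condition concerns the patient, so it most naturally ends the patient's own interviews. The next sentence names caregivers separately and looks ahead to the death. On that view patients are followed until incapacity and caregivers until death, and the only fault is loose wording. It can be added that the words about the patient's death explain the choice of interval and are not a second rule, so there is strictly nothing for the stop rule to contradict. This reading is plausible and may be what was intended. What remains is that the protocol does not state it. If the words about death are only a rationale, the stop rule is the sole instruction on when caregiver interviews end. The Data safety and management plan mentions one participating site and has the DSMB monitor compliance with data collection, which limits inconsistent practice. But compliance cannot be judged against a rule that permits two readings.

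Two stronger inferences are tempting, and the documents do not support them.

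- **That a large, quotable fraction of caregiver data is lost.** Any such figure rests on an assumed incapacity interval and an assumed follow-up time, and it would wrongly be applied to every caregiver, including those whose patient can be interviewed until close to death.
- **That the loss differs between arms.** The plan hypothesises less aggressive care under the intervention, and its sample size section cites lower ventilation (1.6% vs 11.0%) and ICU use (4.1% vs 12.4%) among patients who reported end-of-life care discussions. Such care could itself make a patient uninterviewable, so a difference is conceivable. But nothing in the plan says that the intervention changes the time of incapacity, and the direction is unknown.

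**Conclusion.** The point holds as an unresolved stop rule with a real consequence if followed literally. In dyads whose patient becomes uninterviewable before death, caregiver data for a primary objective would end early for a reason linked to the patient's decline, and the SAP's reassurance about incompleteness does not extend to that kind of missingness under unweighted GEE. The size cannot be determined from the documents: it is about 1 visit per affected dyad if the gap is 3 weeks and about 2 if it is 6, both gaps being assumptions, and 0 or 1 if it is shorter than 3 weeks. The textual finding does not depend on those values. This is a worthwhile and cheap correction. It does not show that the caregiver results are biased or that the bereavement or congruence outcomes are impaired.

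**What to change.** Restate the stop rule separately for each member of the dyad:

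- Patient interviews end at death, withdrawal, loss to follow-up, or when the patient can no longer take part.
- Caregiver interviews continue every 3 weeks until the patient's death, whether or not the patient can still be interviewed, unless the caregiver withdraws or is lost to follow-up.

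The chart review needs no change, since it is already planned after each death.

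The cost is a short rewrite of the stop rule and, for gaps of about 3 to 6 weeks, one or two more interviews per affected caregiver by the existing data collectors. The downside is slightly more burden on those caregivers close to the death; they remain free to decline.

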give terminally ill cancer patients and family caregivers a workbook and a video with educational materials on how to manage common symptoms and a list of available resources, including patient support organizations, as well as support and financial assistance through the hospital's social work department. We hypothesize that using a workbook and a video with content on symptom management alone will not impact the outcomes, but parallelize education received by the control group as much as possible with that of the intervention group. This hypothesis is based on a recent systematic review that found using passive informative material in isolation was an ineffective method for promoting use of ACP.¹¹⁹ The attention-control interventionist will visit and interact with participants in the attention-control group according to the same schedule as for the ACP intervention group to assess their symptom distress and general well-being. Necessary referrals to physicians or social workers will be made for further management.

Randomization

We will enroll and randomly assign eligible dyads of terminally ill cancer patients and their family caregivers into either the ACP intervention or the attention-control group in a 1:1 fashion without stratification. Dyad allocations into the two study arms will be concealed from the personnel responsible for recruiting subjects. A randomization schedule using a computerized random number generator will be prepared in advance by a co-PI ([name]) who will have no contact with any participants throughout the trial and will not be involved in recruiting, enrolling, assigning, assessing, or treating them. The sequence of randomization will be sequentially numbered and sealed in opaque envelopes which will be used later by the PI to allocate participants. The PI will be the only person with access to the allocation schedule during the study and will not be involved in recruiting, enrolling, assessing, or treating participants. The sealed opaque envelopes will not be opened until the PI responsible for assigning participants to the two study arms receives a call from the data collector who has completed the recruitment and initial assessment of a patient-caregiver dyad. The PI will then

open the sealed envelope, assign this dyad to the proper study arm, and forward their information from the envelope to the ACP or attention-control interventionist, accordingly.

Blinding

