Participants, study investigators, data collectors who administer study instruments, and data analysts will be blinded to intervention assignments. All study investigators, research staff (i.e., those who administer the ACP intervention, attention-control care, and outcome measures), and participants will be blinded to trial results until closure of the study. Blinding will be facilitated by both groups (ACP intervention and attention-control) receiving parallel care, preventing data collectors and participants from differentiating between group assignments. To evaluate participant blinding, randomly selected dyads of terminally ill cancer patients and their family caregivers in each study arm will be interviewed by an independent research staff every 3 months to check which arm they believe they are allocated to.

Research fidelity

Research fidelity will be ensured by several strategies. First, the proposed ACP intervention requires an interventionist skilled in the content, techniques, and delivery of the intervention. The interventionist's training will be built on her experience in oncology nursing and palliative care and will be based on her demonstrated competency. The training will include an overview of the study protocol and procedures, a review of the developed workbook and video, and instruction in motivational assessments. The PI will serve as a role model for the interventionist to coach her in assessing and motivating participants at different stages of readiness to engage in ACP and to cooperate with physicians in coordinating and facilitating EOL care discussions on five patient-caregiver dyads as pilot cases. Before the interventionist can formally deliver the intervention to participants, she must successfully demonstrate predefined competencies and consistency in delivering the intervention to promote ACP. Thereafter, the study team will meet biweekly to review the interventionist's notes on intervention sessions and to provide feedback on difficult subject-management issues. Second,

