implementation of randomization, (3) comparability of baseline data between study groups, (4) protocol compliance by research staff, i.e., interventions delivered to each study group and the data collection schemes, (5) protocol compliance by participants, and (6) adverse events (AEs). The DSMB will monitor the progress of subject enrollment every 6 months to ensure adequate subject recruitment and enrollment. To ensure fulfillment of eligibility criteria, the DSMB will monitor the ineligible rate and examine the reasons for refusal to participate in the study, basic demographics, and disease-related characteristics of each recruited dyad of patients and family caregivers.

The DSMB will monitor the dropout rate in each study group every 6 months to detect unexpectedly high dropout rate to clarify or modify the study protocol if necessary.

The study team will record AEs (e.g., complaints of emotional upsets by participating in this study) and submit them monthly in writing to the DSMB, with immediate reporting of serious AEs (SAEs; e.g., suicidal ideation or suicide attempts) to the DSMB and an oncologist with expertise in palliative care. Site reports of AEs/SAEs to its institutional review board (IRB) will be dictated by local requirements.

No data will be analyzed before the study ends. Access to interim results, including baseline data for each group and results from each study arm, will be limited to the DSMB members and the statistician who prepares reports for the DSMB. The DSMB will review study data every 6 months and summarize recommendations for the PI. A summary of reported AEs/SAEs will be sent to the local IRB to ensure that the participating site will be informed of any pertinent safety issues. No favorable or unacceptable benefit-to-risk ratios are expected to find to stop the trial early, thus, no rules for early termination are set.

Statistical analysis plan

All data will be entered into a computer spreadsheet by an administrative assistant. Data will be checked for omissions and outliers to identify potential data entry errors, which will be

clarified with the data enterer. Data will be first descriptively analyzed to check range and distribution of all variables. The baseline equivalence of groups will be tested by differences in their baseline characteristics and outcomes using two-sided Fisher's exact tests and chi-square tests for categorical variables and independent-sample Student's t-tests for continuous variables.

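### Adverse events rest on complaints to an undefined study team, and distress assessment with referral at interventionist visits is written for the control arm only, so any by-arm AE review may be biased in an unknown direction

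*Combined protocol and SAP*

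**What the plan says.** **Capture.** The Data safety and management plan states: "The study team will record AEs (e.g., complaints of emotional upsets by participating in this study) and submit them monthly" to the DSMB. It adds "immediate reporting of serious AEs (SAEs; e.g., suicidal ideation or suicide attempts) to the DSMB" and to an oncologist. It does not say who within the team records, how or when participants are asked, or whether the recorder is blinded. No method of detecting suicidal ideation is written for either arm.

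**Visit content.** Under Components of the proposed study arms, the attention-control interventionist visits on the same schedule as the ACP interventionist, "to assess their symptom distress and general well-being. Necessary referrals to physicians or social workers will be made for further management". ACP contacts, at least monthly until the patient's death, are described in terms of readiness, understanding of prognosis, and preferences. The ACP text on emotional reactions concerns helping physicians to manage them.

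**Blinding.** The Blinding section states: "Participants, study investigators, data collectors who administer study instruments, and data analysts will be blinded to intervention assignments". It continues: "Blinding will be facilitated by both groups (ACP intervention and attention-control) receiving parallel care". The two interventionists are not among the roles listed as blinded to assignment. The Randomization section states: "The PI will be the only person with access to the allocation schedule during the study". Under Research fidelity, "the study team will meet biweekly to review the interventionist's notes on intervention sessions".

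**Scheduled interviews.** Under Data collection procedures: "An every-3-week time frame will be used in this study for repeated QOL and other outcomes assessments", for patients and caregivers alike. Bereavement interviews follow at 1, 3, 6 and 13 months after death.

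**Analysis.** The Statistical analysis plan treats anxiety, depressive symptoms, QOL and grief as efficacy outcomes. It contains no AE table or test.

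**The concern.** Emotional upset from taking part is the plan's own example of an AE, and it is a foreseeable harm when one arm discusses prognosis and shows a video of ICU care and CPR. Upset that is recorded only when someone complains depends on who is listening, what the visit is about, and whether the recorder knows the arm. All three may differ between the arms here. The DSMB could then see a difference that reflects recording, or miss one that is real.

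There is a second consequence. If referral to physicians or social workers is offered at visits in one arm only, it is also a co-intervention acting on the mood and QOL outcomes. The documents do not say whether that is intended.

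**Working it through.** The documents give no AE rate, detection probability or AE power, so there is no figure of the plan's to reproduce. The check is a comparison of the text, followed by an illustration on assumed rates.

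**1. Is capture the same in both arms?**
- *Occasion.* Interventionist visits follow the same schedule in both arms.
- *Content.* Control visits are for assessing symptom distress and general well-being, with referral. ACP visits cover readiness, prognosis and preferences, with no written distress assessment or referral. This is hard to square with parallel care.
- *Recorder.* The interventionists necessarily know the arm. The PI opens the envelopes and holds the schedule. Those who review intervention session notes every two weeks know whose notes they are reading. The blinding statement nevertheless covers study investigators, and the AE recorder is not named.
- *Link to scheduled interviews.* Blinded data collectors see both arms, but no text connects their interviews or scores to AE or SAE reporting.

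**2. How much could unequal capture matter?**
Recorded rate = true rate × detection probability. Recorded ratio = true ratio × (ACP detection ÷ control detection). Every rate below is assumed. Event counts use the planned 231 per arm, one unit per dyad, ignoring attrition.

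| True rate, ACP / control | Detection, ACP / control | Recorded rate | Recorded events | Ratio |
|---|---|---|---|---|
| 30% / 20% | 80% / 80% | 24% / 16% | 55.4 / 37.0 | 1.50 |
| 30% / 20% | 40% / 60% | 12% / 12% | 27.7 / 27.7 | 1.00 |
| 30% / 20% | 60% / 40% | 18% / 8% | 41.6 / 18.5 | 2.25 |
| 10% / 10% | 60% / 80% | 6% / 8% | 13.9 / 18.5 | 0.75 |
| 10% / 10% | 50% / 90% | 5% / 9% | 11.6 / 20.8 | 0.56 |
| 10% / 10% | 30% / 90% | 3% / 9% | 6.9 / 20.8 | 0.33 |
| 10% / 10% | 80% / 50% | 8% / 5% | 18.5 / 11.6 | 1.60 |
| 10% / 10% | 90% / 50% | 9% / 5% | 20.8 / 11.6 | 1.80 |

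The true ACP excess that would be fully hidden is control detection ÷ ACP detection: 80/60 = 1.33, 90/50 = 1.8 and 90/30 = 3.0. Reversing the detection reverses the effect.

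**3. What equal capture would and would not give.**
For recorded rates of 24% and 16%, with 231 per arm and a two-sided 5% test:
- null SE = √(2 × 0.20 × 0.80 / 231) = 0.0372
- alternative SE = √((0.24 × 0.76 + 0.16 × 0.84) / 231) = 0.0370
- power = Φ((0.08 − 1.96 × 0.0372) / 0.0370) = Φ(0.19) ≈ 58%

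Equal capture removes the distortion. It does not make the trial well powered for harms.

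**The case against.** The strongest reply is that emotional harm is measured directly in both arms. Anxiety and depressive symptoms of patients and caregivers are within the primary objectives, outcomes are assessed every 3 weeks by collectors stated to be blinded, and the analysis is by intention to treat. If ACP worsens mood, those outcomes can show it whatever happens to AE recording. This stands, and it limits what is at stake. It does not repair AE reporting, because no rule turns a score or an interview answer into an AE or SAE report.

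A reader might go further than the text allows in four ways.

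- *That the comparison is biased towards making ACP look safe.* This is one plausible direction. But assessing symptom distress is not the same as asking about upset from taking part. Review of session notes is described under the ACP interventionist's training and could raise recorded upset in that arm. Referral in the control arm could lower real distress there.
- *That AE reports are the DSMB's only harm signal.* The DSMB also monitors dropout in each group every 6 months, reviews study data every 6 months and has access to results by arm.
- *That bereaved caregivers have no routine route for harm to be noticed.* Interventionist contact does end at the patient's death, but the bereavement interviews measure QOL, depressive symptoms and grief. What is missing is the link to AE reporting.
- *That data collectors have no AE role, or that the recorders are certainly unblinded.* The first is inferred from silence; the second concerns likely recorders, since none is named.

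Asking about upset could also prompt participants to mention the video or prognosis talks, and so unblind collectors. That risk is real but small: prognostic awareness and EOL discussions are already among the outcomes, and the question can come last.

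**Conclusion.** The point holds as a weakness in ascertainment. AE capture is complaint-based and unstandardised, its recorder is unnamed and may know the arm, and the written content of interventionist visits differs between arms in a way that conflicts with the parallel care on which blinding rests. Any by-arm AE review by the DSMB may therefore be biased, in a direction the documents do not settle. No by-arm AE analysis is specified in the SAP; by-arm review is implied only through the DSMB's access.

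The size cannot be computed from the documents. Under the assumed detection rates, two arms with equal true risk could show a recorded ratio anywhere from 0.33 to 1.80, and a true 30% against 20% could appear as 12% against 12% or as 18% against 8%. These are illustrations, not estimates. The absence of a standard method and the one-sided visit text are certain; the sign is not. The primary efficacy analysis does not depend on AE capture, but a claim of comparable safety by arm would be hard to defend as written.

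**What to change.** 1. Under Data collection procedures and the Data safety and management plan, have the blinded data collectors ask one identical, neutrally worded, scripted AE question, including suicidal ideation, in both arms. Ask it of patients and caregivers at every 3-weekly assessment, and of caregivers at each bereavement interview, after the outcome instruments are complete.
2. Send positive answers through the reporting routes already written, including the immediate route for SAEs.
3. Add to the SAP a by-arm AE table drawn from this source. Present it with confidence intervals, given the limited power. List AEs volunteered to interventionists separately, outside the by-arm rate.
4. Reconcile the attention-control description with the Blinding section on whether distress assessment and referral apply to one arm or both, and count referrals by arm. The choice is for the sponsor.

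Cost: a few minutes per interview at visits already scheduled, brief collector training, some reporting workload, a higher recorded AE count, and a small added risk of unblinding collectors.
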